- 2) Freedom from MALE
- 3) Target vessel and/or bypass patency
- 4) Survival at 1, 3 and 5 years

STUDY DESIGN

This study is a two phase, single-center, non-blinded randomized controlled trial. The first phase of the trial will include 20 patients; 10 assigned to post-operative exercise rehabilitation and 10 to best medical therapy. The primary objective of Phase I is to assess for feasibility and safety of this randomized controlled trial in CLI patients after revascularization. We will assess rate of enrollment, adherence to the exercise regimen and any unforeseen barriers or challenges that patients may encounter with the rehabilitation program.

If Phase I of the trial confirms that the exercise program is feasible and safe for CLI patients post-revascularization, we will proceed with Phase II of the trial. The primary objective for Phase II is to determine if a supervised exercise rehabilitation program will improve walking distance after revascularization compared with patients treated with best medical therapy. Phase II will also compare quality of life outcomes between the two groups.

STUDY POPULATION

The population to be studied in this group is patients with PAD and CLI Fontaine classification III and IV. This means that these patients will have ischemic rest pain in their legs and/or non-healing ischemic ulcers on their feet.

ENROLLMENT

Patients will be identified on a referral basis through our outpatient vascular surgery clinic. The seven practicing vascular surgeons in Calgary will be informed of the current study. Patients who have undergone revascularization for CLI will be identified for consideration of participation in this study within six months of their procedure. All surgical and ischemic wounds to be deemed sufficiently healed prior to assessment for fitness in the study. Once the attending vascular surgeon considers the patient fit to participate, the research coordinator will assess the patient for possible inclusion in the study.

Inclusion Criteria

- 1) Ambulating prior to procedure
- 2) Living independently prior to procedure
- 3) Available to attend all SEP and follow-up appointments
- 4) PAD Fontaine class III and IV (rest pain and tissue loss)
- 5) Entry with consent of vascular surgeon
- 6) Ischemia secondary to TASC A-D lesions identified on imaging (CTA or angiogram)
- 7) Able to understand and sign informed consent
- 8) >18 years of age

Exclusion Criteria

- 1) Confined to wheelchair

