- 2) Patients with exercise tolerance limitations due to other co-morbidities such as cardiorespiratory, musculoskeletal, or peripheral neuropathy. (NYHA class III and IV)
- 3) PAD Fontaine class I and II (asymptomatic, claudication)
- 4) Patients with ongoing tissue loss that limits ambulation
- 5) Patient with previous revascularization procedures
- 6) Patients undergoing revascularization for acute limb ischemia events

SAMPLE SIZE

There are currently no data evaluating outcomes of post-revascularization supervised exercise programs in patients with critical limb ischemia, however these studies have been completed in claudication

patients. Studies on PAD claudication (Fontaine class II) patients who have undergone revascularization followed by SEP have all shown significant improvement in functional capacity compared with best medical therapy alone. These previous studies that showed consistently a 20% greater increase in walking distance in the post-revascularization SEP group compared with Best Medical Therapy (BMT) post-revascularization. Given this previous data, 64 patients are required to have a 80% chance of detecting, with a two-sided significance of 0.05, an increase in the primary outcome measure of a 20% greater increase in distance for the 6MWT in the experimental group compared with the control group. Final sample size will be adjusted for expected attrition.

METHODS

INTERVENTION

Patients included in the study will be identified in the vascular surgery outpatient clinic or through Emergency department as requiring revascularization secondary to critical limb ischemia. Patients will be approached regarding study participation prior to the revascularization procedure. After eligibility is confirmed and patients have signed informed consent, patients will be randomized to one of two groups:

- 1) Best Medical Therapy (BMT)
- 2) BMT + Supervised Exercise Program (SEP)

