Microsoft Excel will be used to generate a block randomization sequence for Phase I (20 patients) followed by a block randomization sequence for Phase II (44 patients) of the study. Patients who are eligible to participate in the study will be stratified by sex and randomized to either SEP or BMT. Block sizes of 4 and 6 will be used to prevent anticipation of the randomization sequence.

ALLOCATION CONCEALMENT

Once the random block sequence has been generated, allocation cards will be created and sealed in sequentially numbered opaque envelopes. The envelopes will be stored in a secured filing cabinet in the vascular surgery research office. The envelopes will be opened sequentially after a patient consents to participate in the study.

DATA COLLECTION

No study data will be collected until patients have reviewed and signed the informed consent. Opportunity to ask questions and have time independent from study team will be provided.

Data will be recorded using Excel spreadsheets. Medical outcomes and complications will be tracked using Vascubase software. Data will be stored on Alberta Health Services computers to maintain patient confidentiality.

STATISTICAL ANALYSIS

Normally distributed data will be presented as mean \pm SD. Results at baseline and 12 weeks will be compared using a paired t-test. For data that is not normally distributed, comparisons will be performed using a non-parametric Mann-Whitney test. Comparisons will be accepted as statistically significant at 95% confidence level ($p \leq 0.05$). STATA software will be used for statistical analysis.

ETHICAL CONSIDERATIONS

Patients who are randomized to the SEP group will be provided with tri-weekly visits for supervised exercise guidance and support. Patients will receive reimbursement for travel to and from the exercise facility. This will include refunds for gas, parking or other required transportation (taxi, public transport, etc).

FOLLOW UP OF PATIENTS WITHDRAWN FROM STUDY

Patients who withdraw or do not complete the program will be contacted and interviewed at the end of the 12 week study period to understand why they were unable to complete the training program.

LIMITATIONS

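### The trial randomizes by phase and by sex, and reaches its 64 patients only by counting both phases, yet the analysis uses neither factor

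*Combined protocol and SAP*

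**What the plan says.** All references are to the combined protocol and SAP.

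- **RANDOMIZATION** sets up "a block randomization sequence for Phase I (20 patients) followed by a block randomization sequence for Phase II (44 patients"). Patients are also stratified by sex. Phase is therefore a randomization stratum by construction, and sex is one by name.
- **SAMPLE SIZE** states that "64 patients are required to have a 80% chance of detecting" the target difference, "with a two-sided significance of 0.05". The target is "a 20% greater increase in distance for the 6MWT in the experimental group compared with the control group". No SD is given. Attrition is left for later: "Final sample size will be adjusted for expected attrition".
- **STUDY DESIGN** gives the phases different main aims. Phase I (20 patients, 10 per arm) looks at feasibility and safety, including enrolment, adherence and "any unforeseen barriers or challenges that patients may encounter with the rehabilitation program". Phase II opens if Phase I shows that the programme can be delivered safely. "The primary objective for Phase II is to determine if a supervised exercise rehabilitation program will improve walking distance". The trial is not blinded.
- **STATISTICAL ANALYSIS** names a paired t-test of baseline against 12 weeks, and a Mann-Whitney test for data that are not normal. It mentions neither phase nor sex. It does not say whether Phase I patients enter the walking comparison, or what happens to their data if the programme is altered after Phase I.

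**The concern.** An analysis should reflect the way patients were randomized. Here two factors define the randomization lists and neither appears in the analysis. If patients in the two phases change by different amounts on average, that difference stays in the error term and reduces power.

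Two related gaps come from the same silence. The plan does not say which patients form the efficacy sample, and the choice matters because 44 is well short of 64. It also has no rule for a programme that is modified after Phase I. Such a change is not announced, but it is foreseeable when one task of Phase I is to find barriers. Finally, the trial is open and nothing keeps the Phase I walking results by arm from the team that decides whether to go on.

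**Working it through.** **Inputs from the document:** 64 patients, 80% power, two-sided 0.05 (SAMPLE SIZE); 20 and 44 patients by phase (RANDOMIZATION). **Assumed:** equal arms, normal outcomes with a common within-phase SD, and the ranges given below.

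**1. The plan's own figure.** 20 + 44 = 64, so the split matches the requirement. The 64 cannot be derived forward, because no SD is stated. Solving backwards for 32 per arm with the noncentral t gives d = 0.711. The normal approximation gives d = (1.960 + 0.842) × √(2/32) = 0.700. If the 20% is read as 20 percentage points, d = 0.711 implies an SD of 20/0.711 = 28.1 points. All power figures below use d = 0.711, with this SD taken as the within-phase SD.

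**2. Cost of ignoring phase.** Let mean change differ between phases by s SD. With p = 20/64 = 0.3125, the variance in an analysis without phase is 1 + p(1 − p)s² = 1 + 0.2148s², and the effective d is 0.711 divided by its square root.

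| s (assumed) | Variance factor | Effective d | Power, 32 per arm |
|---|---|---|---|
| 0 | 1.000 | 0.711 | 80.0% |
| 0.25 | 1.013 | 0.707 | 79.5% |
| 0.5 | 1.054 | 0.693 | 77.9% |
| 1 | 1.215 | 0.646 | 72.0% |

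**3. Cost of including the factors.** With d and n unchanged, error df goes from 62 to 61 with phase (power 79.98%) and to 60 with phase and sex (79.96%).

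**4. If efficacy were tested in Phase II alone.** With 22 per arm and d = 0.711, power is 63.5% (64.2% by the normal approximation at d = 0.700). Phase II would need 64 patients of its own, so 20 + 64 = 84 in all before attrition.

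**5. If the programme changed and Phase I patients had only a fraction f of the Phase II effect.** The pooled effect is d × (20f + 44)/64.

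| f (assumed) | Pooled fraction | Pooled d | Power, 64 pooled |
|---|---|---|---|
| 0.75 | 0.922 | 0.656 | 73% |
| 0.50 | 0.844 | 0.600 | 66% |
| 0.25 | 0.766 | 0.545 | 57% |
| 0 | 0.688 | 0.489 | 49% |

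Set against the 63.5% of step 4, pooling stays the more powerful choice until f falls below about 0.43.

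**6. If continuation depended on Phase I walking.** Suppose the trial went on only when Phase I favoured exercise, and there were no true effect. The pooled estimate in continuing trials is then shifted by (20/64) × √(2/10) × √(2/π) = 0.3125 × 0.447 × 0.798 = 0.11 SD. By simulation, a significant result favouring exercise occurs in 4.7% of continuing trials, and a significant result in either direction in 5.0%. Counted over all trials started, the rates are 2.4% and 2.5%.

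**The case against.** **Pooling is never stated.** This is correct: it is inferred from 20 + 44 = 64. The other reading does not rescue the plan, because Phase II alone would then be tested with 44 patients against a stated need for 64. Either way the analysis set has to be named.

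**Leaving out phase does no harm to validity.** This also stands. With arms allocated about 1:1 within each phase, a difference between phases falls on both arms alike. The loss is precision, and it is small unless the phases differ markedly.

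**A reader might infer that pooling makes the result meaningless.** The document does not support that. Nowhere does it say that the programme will change. The interviews that collect barriers (PRE/POST TESTING) are planned for the exercise group as such and are not tied to Phase I. Even after a change, the pooled estimate is a weighted average over two versions and still a valid test of no effect. Nor would reporting by phase restore power: under a half effect in Phase I, the 44 alone give 63.5% against 65.7% pooled, and in Phase I by itself the 95% half-width is about 0.94 SD (2.101 × √0.2).

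**A reader might also infer that the false-positive rate is doubled, from 2.5% to 4.7%.** That figure requires a rule to continue on walking results, whereas STUDY DESIGN makes continuation depend on feasibility and safety. It is also one-sided and conditional on going on. The two-sided rate among continuing trials is nominal, and the overall rates are not inflated. What remains is that no written restriction keeps by-arm walking results from an unblinded team.

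**A phase term presupposes a between-arm model.** True. STATISTICAL ANALYSIS describes tests but no such model, so one has to be written in. A phase term also cures neither dilution nor selection; those need the separate statements under the fix.

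**Conclusion.** The point holds as one of precision and of completeness, not of bias. The lists are drawn by phase and sex, and the analysis uses neither. Ignoring phase lowers power from 80% to about 79%, 78% or 72% for phase differences of 0.25, 0.5 or 1 SD. These differences are assumed, and d = 0.711 is back-solved, so the figures show scale and are not predictions. The use of Phase I patients for efficacy is inferred from the arithmetic and should be confirmed in words.

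Dilution after a programme change, and selection through an early look at walking, are possibilities that the plan leaves open. They are not features of it. They justify a sentence each, but not a claim that the planned comparison is biased or that its type I error is inflated.

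**What to change.** 1. **RANDOMIZATION and STATISTICAL ANALYSIS:** state that all 64 patients enter the 6-minute walk comparison. Compare change between arms in a model with phase and sex as factors, and show the arm difference by phase descriptively. Cost: one degree of freedom per factor, with power 79.98% after the phase term.
2. **STUDY DESIGN:** state that walking and quality-of-life results are not compared by arm until Phase II ends. This makes the existing feasibility-and-safety condition effective in an open trial. Cost: no early look at efficacy.
3. **STATISTICAL ANALYSIS:** state that, if the programme is changed after Phase I, the pooled result will be reported as an average over two versions and 80% power will not be claimed for it. Cost: the power claim in that event. If the sponsor would rather rest the efficacy test on Phase II alone, that phase has to be re-sized, since 44 patients give about 64% power at the implied effect.

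### Stratification by sex is stated, but neither the sequence-and-envelope procedure nor the named tests contain a step that uses sex

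*Combined protocol and SAP*

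**What the plan says.** All of the relevant text is in the combined protocol and SAP.

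- **Randomization, the factor:** "Patients who are eligible to participate in the study will be stratified by sex". No other stratification factor is named anywhere in the plan.
- **Randomization, the sequences:** the spreadsheet is to produce one sequence per phase, of length 20 and then 44, with blocks of 4 and 6 mixed so that the next assignment cannot be guessed. No sequence per sex is mentioned.
- **Allocation Concealment:** cards made from the sequence, which is referred to in the singular, go into numbered opaque envelopes. The rule for drawing them is: "The envelopes will be opened sequentially after a patient consents to participate in the study". The patient's sex plays no part in it.
- **Statistical Analysis:** the parametric method is given as "Results at baseline and 12 weeks will be compared using a paired t-test". A Mann-Whitney test is the fallback for non-normal data. Neither method has a sex term or a sex stratum.
- **Study Design:** Phase I is to have 10 patients in each arm.
- **Limitations:** the lack of stratification by anatomical level is acknowledged. Nothing is said there about sex.

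**The concern.** Stratified randomisation needs a separate sequence for each stratum and a rule that sends each patient to the right one. The document names the factor and supplies neither. Someone opening envelopes strictly in number order, from the sequences described, would never need to know the patient's sex.

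Two things are at stake.

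1. **Allocation.** If one list per phase is used, the trial would be reported as stratified when it was not, and it would lack the protection against chance imbalance that stratification gives. The person holding the envelopes would also have two instructions, stratify and open in order, with nothing to show how they fit together.
2. **Analysis.** If separate lists are used, a test that ignores sex does not match the design. Stratification removes sex-related variation from the arm difference, but an unadjusted standard error still counts it.

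**Working it through.** **The plan's own figures.** 20 + 44 = 64, the total in Sample Size. No SD is given, so 64 cannot be re-derived from the document. With 32 per arm, 80% power and two-sided 0.05, it implies a standardised difference of (1.96 + 0.842) × √(2/32) = 0.70, which is used below. Blocks of 4 and 6 fill both sequences exactly (20 = 2×4 + 2×6 or 5×4; 44 = 5×4 + 4×6, among others). A single list per phase can therefore give exactly 10:10 and 22:22. Two sex strata need not. This is consistent with one list but does not prove it.

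**Inputs that are assumptions.** Share of women p = 25%, 35% or 45%. Sex difference on the analysed outcome g = 0.5 to 0.8 SD. The document gives neither.

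**Step 1: balance with one list per phase.** Allocation does not depend on sex and each arm has 32 patients, so the number of women in each arm is an independent binomial (32, p). The difference D has variance 64·p·(1−p). With a continuity correction, P(|D| ≥ 4) ≈ 2·[1 − Φ(3.5/SD)] and P(|D| ≥ 6) ≈ 2·[1 − Φ(5.5/SD)].

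| p | SD of D | P(4 or more women apart) | P(6 or more women apart) |
|---|---|---|---|
| 25% | √12.00 = 3.46 | 31% | 11% |
| 35% | √14.56 = 3.82 | 36% | 15% |
| 45% | √15.84 = 3.98 | 38% | 17% |

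Exact binomial sums and simulation of the permuted blocks agree to within about one percentage point.

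**Step 2: balance with separate lists by sex within phase.** Simulation with blocks of 4 and 6 in random order gives 4 or more women apart in about 1% of trials, and 6 or more in about 0%. Phase I splits exactly 10:10 in about 55% of runs, and 12:8 or worse in about 2%.

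**Step 3: an unadjusted between-arm test after true stratification.** If sex is balanced, the true variance of the arm difference reflects only within-sex variance (set to 1). The unadjusted test uses about 1 + g²·p·(1−p). At p = 35%, p·(1−p) = 0.2275.

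- g = 0.5: √(1 + 0.25 × 0.2275) = 1.028. The effective critical value is 1.96 × 1.028 = 2.015, so type I error is about 4.4%.
- g = 0.8: √(1 + 0.64 × 0.2275) = 1.070. The effective critical value is 1.96 × 1.070 = 2.098, so type I error is about 3.6%.

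Simulations at N = 64 gave 3.9-4.2% and 3.5-3.6%. At a standardised difference of 0.70, power was about 77% (g = 0.5) and 74-75% (g = 0.8) unadjusted, against about 78% with sex in the model.

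**Step 4: an unadjusted test with one list.** Type I error was 5.1-5.6% across runs, which is nominal within simulation error. The comparison stays valid.

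**The case against.** The strongest reply is that this is a reporting gap in a short pilot protocol. Consecutive numbering and opening in order fit one envelope set per sex as well as they fit a single set. Separate lists are not described, but nothing excludes them. That stands, and it limits the point in four ways.

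- A reader might infer that the trial is incapable of stratifying. The document does not support this. It shows only that the steps as written do not use sex.
- A reader might infer that the protocol promises arms balanced by sex and fails to deliver. No sentence makes that promise; it is at most implied by the word stratified. The stated purpose of the varying block sizes is to keep the sequence unpredictable.
- A reader might link the missing sex term to imbalance. Allocation sets balance; the analysis can neither create nor remove it. These are two separate gaps.
- A reader might convert imbalance into metres, for example 6/32 of an assumed 30-60 m sex difference in walking distance, or about 6-11 m. The primary outcome in Outcome Measures is a change, and a stable difference in level between the sexes largely cancels in a change. Bias would need the sexes to improve by different amounts, and the document gives no figure for that.

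It is also fair to say that the harm is modest either way. One list still gives an unbiased comparison, and ignoring sex after true stratification errs on the safe side.

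The reply does not remove the inconsistency. The factor is named, no step applies it, and the analysis omits it.

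**Conclusion.** The point holds as an unresolved inconsistency with a cheap remedy. Followed literally, the procedure is valid but unstratified. It leaves the arms 4 or more women apart in roughly 31-38% of trials, against about 1% with separate lists, assuming 25-45% women. If separate lists are used, omitting sex makes an unadjusted between-arm test slightly conservative, with type I error of about 3.5-4.5%, and costs roughly 1 to 4 points of power. Those figures assume a sex difference of 0.5-0.8 SD and 35% women. With no sex difference, the loss is nil. No inflated false-positive risk is shown, and the documents do not support a statement that the trial's result would be biased.

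**What to change.** 1. In Randomization, specify four sequences: men and women, within Phase I and within Phase II, each with blocks of 4 and 6 in random order.
2. In Allocation Concealment, specify a separately numbered envelope set for each sequence. Record the patient's sex after consent, then open the next envelope in that patient's own set.
3. In Statistical Analysis, include sex as a covariate in the between-arm analysis of the 6MWT. The paired t-test named there compares within patients, so a between-arm model must be stated first; that is a separate point.
4. If separate lists are not intended, delete the statement on stratification.

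The cost is a few spreadsheet columns, labelled envelope sets and one covariate. Phase I may come out 11:9 rather than exactly 10:10, so 10 per arm becomes a target; that is only a matter of wording. The change has to be made before the envelopes for the phase concerned are prepared, because allocations already made cannot be re-stratified.

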All of the studies described here were primarily treating patients with IC. Only Jakubseviciene et al. (2014) and Badger et al (2007) included patients with PAD and rest pain. **To date, there are no studies dedicated to patients with critical limb ischemia comparing outcomes for exercise training versus BMT post revascularization.** All of these studies exclusively evaluate patient-related outcomes such as walking distance, functional capacity and QoL. While these parameters are tremendously important, there are no data regarding how post treatment exercise training may affect amputation rates, readmission to hospital or reintervention rates in the PAD patients with critical limb ischemia. Such parameters are defined as major adverse limb events (MALE).

Health Economics

The 1992 Canadian Heart Health survey showed a significant economic benefit for all participants who participated in an exercise program, both supervised and unsupervised. In patients with known cardiovascular disease, a SEP showed significant cost savings for years of life (Lowenstein, Coupal, Zowall, & Grover, 2000). In patients with IC, studies have shown that SEP is more cost- effective than endovascular interventions as a primary treatment modality. Furthermore, although the initial cost of SEP may be slightly greater when compared with HEP, it has greater cost-effectiveness up to five years (Fokkenrood et al., 2014; Reynolds et al., 2014; Spronk et al., 2009). There has been no data evaluating the cost benefits associated with CLI patients who have undergone revascularization. Given that re-interventions are frequent (and costly), post revascularization exercise training may be of significant and substantial benefit in patients with CLI.

Summary

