Exercise training is a proven effective treatment for patients with PAD with significant functional, psychosocial and economic benefits. In current practice, there are no guidelines for exercise training and rehabilitation for patients who have progressed to CLI and have undergone revascularization. While it may be a challenge given the severity of disease and number of comorbidities in this patient population, it is great a disservice to deny these patients exercise rehabilitation given the possible advantages for their functional capacity, quality of life and even survival. Randomized controlled trials (RCT) are necessary to determine the precise role of exercise rehabilitation in patients with CLI. An RCT will provide guidance for regarding exercise tolerance, appropriate exercise modalities as well as the challenges and benefits of exercise rehabilitation in this critically ill population.

Objectives:

The aim of this pilot study is to develop a better understanding of the role for supervised exercise rehabilitation programs (SEP) in CLI patients after revascularization.

Our key objectives are as follows:

- 1) Our primary objective is to show that a 12-week SEP will improve functional capacity and quality of life in patients with CLI after revascularization. We will assess the feasibility for completion of a 12-week SEP in patients with CLI who have undergone revascularization.
- 2) Our secondary objective is to monitor major adverse limb events (MALE) and survival in patients who complete a 12-week SEP after revascularization.

Hypotheses:

- 1) We hypothesize that PAD-CLI patients who participate in an exercise rehabilitation after they have undergone revascularization will have a greater improvement in functional capacity and quality of life compared with patients treated with best medical therapy alone.
- 2) We hypothesize that PAD-CLI patients who participate in an exercise rehabilitation after they have undergone revascularization will have fewer MALE and improved survival compared with patients treated with best medical therapy alone.

OUTCOME MEASURES:

Primary outcome measures:

Our primary outcome measure for this project will be change in functional capacity as measured by a 6-minute walking test (6MWT) or maximal pain-free walking distance on a treadmill.

Secondary outcome measures:

- 1) Quality of life based on questionnaires validated for patients with PAD, the SF-36 and VQ6
- 2) Completion of a 12 week supervised exercise program

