The patient will undergo the revascularization procedure and any adjunctive treatment such as wound care/debridement or minor amputation (toes, trans-metatarsal amputation). All surgical wounds and ischemic ulcers will require assessment by attending surgeon for adequate healing prior to initial assessment at the exercise facility. This may require as little as one week or as long as 6 weeks to achieve sufficient healing. The exercise assessment and program delivery will take place at a cardiac rehabilitation facility that has extensive experience in managing patients with cardiovascular disease and PAD in the post op setting.

Best medical therapy

All patients in the study will be assessed and monitored by internal medicine specialists as well as the vascular surgery team for management of PAD risk factors including, but not limited to: hypertension, smoking cessation, dyslipidemia and diabetes. The patients will be prescribed appropriate pharmacotherapy as deemed appropriate. A typical regimen for these patients may include antiplatelet agents, B-blockers, ACE-inhibitors, and diabetic control agents. Patients will be advised to target a systolic blood pressure of $\leq 140\text{mmHg}$ ($\leq 130\text{mmHg}$ if diabetic), $\text{LDL-C} < 2.0\text{ mmol/L}$ and a $\text{HbA1c} \leq 7\%$. They will also be given information regarding engaging in exercise and physical activity three to five times per week. Patients will be asked to keep a log of their physical activity for the 12-week duration of the study. The patients will be provided with a log to record their physical activity.

Standardized Exercise Program Regimen

In addition to best medical therapy management, the patients randomized to the SEP arm of the trial will attend a supervised exercise program at a cardiac rehabilitation facility at least two times per week for 12 weeks. Programs will be designed and coordinated by an exercise physiologist. All patient expenses for the program will be covered by the study budget. There will be no financial burden placed on the participants.

MEASUREMENTS

General health metrics will be collected at the start and end of the 12-week intervention period. This includes height, weight, BMI, blood pressure and resting heart rate. We will record medications,

smoking history status, presence of diabetes, dyslipidemia, cardiovascular disease history including previous myocardial infarct (MI) and stroke/transient ischemic attack.

PRE/POST TESTING

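### Phase I must show that supervised exercise is safe, but outpatient wound problems and cardiovascular events without admission are not listed outcomes and are plausibly noticed more often in the exercise arm

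*Combined protocol and SAP*

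**What the plan says.** STUDY DESIGN sets the purpose of the first 20 patients, 10 per arm: "The primary objective of Phase I is to assess for feasibility and safety of this randomized controlled trial in CLI patients after revascularization". Phase II follows on a condition: "If Phase I of the trial confirms that the exercise program is feasible and safe for CLI patients post-revascularization". The measures then named are these: "We will assess rate of enrollment, adherence to the exercise regimen and any unforeseen barriers or challenges that patients may encounter".

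OUTCOME MEASURES lists walking distance, quality of life, programme completion, freedom from MALE, patency and survival. The Hypotheses section expects that exercising patients "will have fewer MALE and improved survival compared with patients treated with best medical therapy alone". The background section on exercise after revascularization gives the content of MALE as amputation, "readmission to hospital or reintervention rates in the PAD patients with critical limb ischemia. Such parameters are defined as major adverse limb events (MALE"). It sets no limit on the cause of readmission.

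Under DATA COLLECTION, "Medical outcomes and complications will be tracked using Vascubase software". No event definition, schedule or window is attached. STATISTICAL ANALYSIS describes a paired t-test and a Mann-Whitney test, and no summary of events.

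On contact, SEP patients "will attend a supervised exercise program at a cardiac rehabilitation facility at least two times per week for 12 weeks", and the Quality of Life section adds an interview and survey at mid-term and completion for SEP only. Under Best medical therapy, internists and the vascular team monitor risk factors in all patients, with no visit frequency given. Duplex at 2 and 12 weeks and ABI at 12 weeks are not tied to an arm.

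**The concern.** The decision to open Phase II needs a judgement that the programme is safe, and with 10 patients per arm that judgement will rest on a handful of events. The listed outcomes catch death and major limb events. They do not catch a wound that reopens and is dressed in clinic, a new ulcer, or a cardiovascular event that never reaches a ward. Yet wound problems are a natural worry when patients with recent tissue loss start exercising.

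These lesser events depend on someone noticing or asking. A patient seen twice a week by rehabilitation staff has more chances to mention one than a patient with no scheduled contact. If they surface mainly in SEP, the programme can look less safe than it is. If nobody tabulates them by arm, a real excess can pass unseen. An event never asked about in BMT cannot be recovered at analysis.

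**Working it through.** The plan gives no event rate, detection rate or safety figure, so there is nothing of its own to reproduce. The inputs from the documents are 10 patients per arm in Phase I (STUDY DESIGN), 64 in total and so 32 per arm (SAMPLE SIZE), and the SEP contact schedule. All event and detection rates below are assumptions.

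**Step 1, contacts.** SEP has at least 2 × 12 = 24 supervised visits. If the tri-weekly visits under ETHICAL CONSIDERATIONS mean three a week, it has 3 × 12 = 36. The number of BMT contacts over the same 12 weeks is not stated.

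**Step 2, which events are exposed.**
- Death, amputation, reintervention and patency are listed outcomes, with no arm-specific collection.
- Myocardial infarction, stroke or heart failure that leads to admission normally reaches hospital in either arm, and can count as a readmission within MALE.
- Outpatient wound problems and non-admitted cardiovascular events have neither safeguard.

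**Step 3, effect of unequal noticing when the true risk is equal.** Recorded counts are taken as independent binomials with n = 10 per arm and probability = true rate × detection. For example, 0.10 × 0.9 = 0.09 in SEP and 0.10 × 0.5 = 0.05 in BMT, an expected 0.9 versus 0.5 events.

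| True rate | Detection SEP / BMT | SEP more | Tie | SEP fewer |
|---|---|---|---|---|
| 10% | 90% / 90% | 33% | 33% | 33% |
| 10% | 90% / 80% | 36% | 34% | 30% |
| 10% | 80% / 60% | 37% | 38% | 25% |
| 10% | 90% / 50% | 44% | 37% | 19% |
| 5% | 90% / 50% | 30% | 55% | 15% |
| 20% | 90% / 50% | 57% | 23% | 19% |

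**Step 4, comparison with sampling error.** At a 10% true rate and 90/50 detection the bias in the risk difference is 9 − 5 = 4 percentage points; at a 20% true rate it is 18 − 10 = 8. The exact 95% half-width for the risk difference (unconditional, score statistic) is about 31 points at 0/10 versus 0/10 and 37 at 1/10 versus 1/10. With 32 per arm it is about 15 points at 2/32 each and 17 at 3/32 each. The bias is well inside the noise, so it could not be identified afterwards.

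**Step 5, what 10 patients can show.** The chance of seeing at least one event in an arm is 1 − (1 − p)^n. For p = 2%, 5% and 10% this is 18%, 40% and 65% with n = 10, and 48%, 81% and 97% with n = 32. Any safety table from Phase I can only be descriptive.

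**The case against.** A reader might infer that all non-fatal cardiovascular events are under-recorded in BMT. The documents do not support that. Admitted events reach hospital whichever arm the patient is in, readmission is part of MALE without a limit on cause, and complications are tracked without restriction by arm. MEASUREMENTS also says that a history of infarction and stroke or TIA will be recorded, close to a sentence on collection at the start and end of the 12 weeks. If it applies at both visits, new events of that kind may already be asked about equally. This objection stands, and the point is confined to events without admission.

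Closer observation of wounds is also only inferred. No wound inspection is stated for SEP sessions, the SEP interview is about challenges of rehabilitation, and both arms share specialist monitoring and duplex visits. The 90/50 detection split has no basis in the documents, and at 90/80 the picture is close to equal detection. That stands as a limit on size, but it does not supply the missing question in BMT.

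The exclusions ("Patients with exercise tolerance limitations due to other co-morbidities such as cardiorespiratory, musculoskeletal, or peripheral neuropathy", and tissue loss limiting ambulation) and surgeon-assessed healing lower event rates in both arms. They do not equalise how events are learned.

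Finally, the lack of an event table applies to MALE and survival too, so on its own it is missing detail. A 12-week question relies on recall and sets no threshold for calling the programme safe. Both remarks are fair. With 10 per arm the decision will remain a clinical judgement, and the question makes its basis more comparable.

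**Conclusion.** The point holds in a limited form. Safety is a condition for Phase II, no safety outcome is named beyond MALE, patency and survival, and two kinds of lesser event fall outside those. The contact schedule makes it plausible that SEP will record more of them. The size is unknown: under assumed detection from 90/80 to 90/50 and a true rate of 10% in both arms, the chance of SEP showing the higher count moves from 33% to between 36% and 44%. This is smaller than sampling error at 10 per arm.

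A reader might go further and conclude that safety data are not collected, or that the Phase II decision will be biased against exercise. Neither follows. Complications are tracked, and differential detection is an inference that no stated rate supports. Conclusions on admission, amputation, reintervention, patency and death are largely unaffected by arm. Importance is minor to moderate; the case for acting is that the remedy is cheap and the data cannot be obtained later.

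**What to change.** - **Collection.** At the existing 12-week visit, ask both arms the same question on new myocardial infarction, stroke or TIA, heart-failure admission, and reopened wound or new ulcer since randomization, including episodes that have since healed. Record wound status on the treated leg. Starting at randomization works whether patients are randomized before the procedure (INTERVENTION) or identified after it (ENROLLMENT).
- **Withdrawn patients.** Ask the same question at the 12-week contact for patients of either arm. That contact is worded around the training programme, so state that it includes BMT.
- **Outcome and analysis.** List this under OUTCOME MEASURES as a secondary safety outcome. In STATISTICAL ANALYSIS, add the number and proportion of patients with events by randomized arm, descriptive only, available for the Phase II decision. Note events known only from SEP sessions or interviews.

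The cost is some protocol wording, slight extra data entry and possibly calls to withdrawn BMT patients; no new visit or procedure is needed. Recall may remain somewhat better in SEP, and intervals will be wide, so the table can inform the decision but cannot show that the arms are equally safe. Splitting readmissions by cause or adding a second analysis window is optional.
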